## Version History

Version #	Approval Date	Significant Changes from Previous Version
1.1		
 
1. Added anti-drug antibodies (see Sections 6.2.4 and 6.3.2, and Tables 1 and 2).
 
2. Added specific genotypes that will be tested if an osteopetrosis related mutation has not been previously identified (see Section 6.3.2 and Tables 1 and 2).
 
3. Added justification for maximum dose and criteria to de-escalate dose (see Sections 3 and 6.3.6)
 
4. Added the following withdrawal criteria: subject contracts an intercurrent illness that requires treatment not consistent with the protocol requirements. (see Section 5.4.8)
 
5. Added specification that the method used to calculate body surface area (BSA) is the Mosteller method (see Section 6.3.6).
 
6. Added exclusion criteria of history of hematopoietic cell transplantation (HCT)
 
7. Additional details on ex vivo assays were added to Section 6.3.5.5.
 

1.2	22Mar2016	Study subject compensation was clarified in section 6.9.
1.3	12Apr2016	
 
1. Added that screening will be within 3 months of baseline visit
 
2. Added 25-hydroxy vitamin D level at 6 week lab visit
 
3. Added additional instructions for processing blood and urine specimens (see Table 2 and sections 6.2.2, 6.2.3, and 6.2.4)
 
4. Safety monitor was changed due to conflict of interest for [name] (see Appendix A)
 

1.4	7Sept2016	Added collection of a PAXgene tube for RNA extraction and buffy coat to be stored for future DNA studies (see Table 2, and Sections 6.3.2 and 9.6).
1.5	22Nov2016	Added “thalassemia or other hemoglobinopathy” to the exclusion criteria.
1.6	8Mar2017	
 
1. Updated PI contact info
 
2. Changed UMN site PI due to [name] leaving UMN.
 
3. Section 5.4.4: Language was clarified to indicate that HCT cannot be expected to occur within 12 months of starting this study.
 
4. Section 5.4.6: Added exclusion criteria of a left ventricular ejection fraction of <30% to ensure consistency in using the screening ECHO results in determining enrollment in study.
 
5. Section 6.3.2: Corrected labs to be collected at weeks 4 and 6 and month 9. This paragraph is now consistent with informed consent document and other areas in this protocol.
 
6. Section 6.3.2: Added adults ≥18 years old to the vitamin D and calcium treatment plans.
 

1.7	10Aug2017	
 
Section 6.3.4.2: Language was clarified to add 3% and 38% sites of the non-dominant radius.
 
Clarification of timing of RNA and DNA sample collection was added to Table 1.
 
Section 6.9: Clarification of subject compensation between LA Biomed and University of Minnesota sites.
 

1.8	13Dec2017	
 
Section 6.2.2: Clarification of DNA, RNA and Urine collection, processing, shipping and Storage.
 
Section 6.9: Correction of subject compensation which will be the same at each site.
 
Section 6.3.6: Extended duration for study drug titration to maximum dose and added recommendations for medications that may be used to treat adverse effects of the study drug.
 
Changed site PI and clinical coordinator at UMN, and clinical coordinator at LA BioMed.
 
Improved language in sections 5.4.4, 6.2.2, 6.2.3, and 8.2 to improve clarity.
 
Section 6.2.3: Changed the shipping contact and address for samples sent to UMN.
 

## Study Summary

Title	Open-label Phase 1/2 Study with a Single Arm of Interferon Gamma-1b Treatment of Osteopetrosis
Study Sponsor	[name], MS Assistant Professor, Pediatric Endocrinology David Geffen School of Medicine Los Angeles Biomedical Research Institute at Harbor-UCLA Medical Center
Principal Investigator (PI)	[name], MS Assistant Professor, Pediatric Endocrinology David Geffen School of Medicine Los Angeles Biomedical Research Institute at Harbor-UCLA Medical Center
Study Design	multi-center open-label phase 1/2 clinical trial
Study Duration	Subjects will participate in the study for 1 year. It is expected that enrollment will be completed in 18 months and the last subject will complete the protocol 2.5 years after study initiation.
Study Center(s)	
 
1. LABioMed at Harbor-UCLA [name] [name]
 
2. University of Minnesota [name] [name]
 

Study Objectives	
 
1. To determine the feasibility and tolerability of interferon gamma-1b treatment in patients with intermediate osteopetrosis.
 
2. To determine the safety and efficacy of interferon gamma-1b in patients with intermediate osteopetrosis.
 

Study Endpoints	
Primary Endpoint: The primary objective of this pilot study is to determine the feasibility and tolerability of interferon gamma-1b treatment for 1 year in patients with intermediate osteopetrosis. Specifically, i) the ability to enroll patients, and ii) continued treatment throughout the 1-year observational period.
 
Secondary Endpoints: The secondary objectives of this study will focus on change in immunologic and hematologic function, bone mineral density and osteoclast function, physical function and quality of life.

Number of Subjects	10
Main Inclusion Criteria	
 
• Intermediate Osteopetrosis, defined as: 
 
○ Anemia, or
 
○ Neutropenia, or
 
○ <math>\geq 1</math> serious infection over prior year defined as requiring hospitalization and/or IV antibiotics, or
 
○ History of impaired bone healing
 
 
 
• Age <math>> 1</math> year
 

Duration of Observation	1 year
Statistical Methods	Descriptive analyses of baseline characteristics and outcomes will include means and standard deviations for continuous variables and frequencies for categorical variables. Confidence intervals and P-values will be based on a t-distribution. Statistical significance will be considered as $p < 0.05$ . The primary endpoint and safety analyses will be primarily descriptive reporting the number and percentage of compliance and AEs. The secondary endpoints for hematologic function, immune function, bone mineral density, physical function and quality of life will be evaluated by paired t-tests or chi-squared to evaluate change from baseline to 12 months. Secondary endpoints related to in vitro osteoclast assays will be descriptive.

## List of Abbreviations

AE	Adverse Event
BMI	Body Mass Index
CAII	Carbonic Anhydrase II
CBCD	Complete Blood Count with Differential
CFR	Code of Federal Regulations
CHQ-PF50	Children's Health Questionnaire-Parent Form 50
CLCN7	Chloride Channel 7
CNS	Central Nervous System
CRF	Case Report Form
CRP	C-Reactive Protein
CTSI	Clinical and Translational Science Institute
DNA	Deoxyribonucleic Acid
DSMB	Data and Safety Monitoring Board
EDTA	Ethylenediaminetetraacetic Acid
ELISA	Enzyme Linked Immunosorbent Assay
FDA	Food and Drug Administration
GCP	Good Clinical Practice
HCT	Hematopoietic Cell Transplantation
HIPAA	Health Insurance Portability and Accountability Act of 1996
IATA	International Air Transport Association
ICH	International Conference on Harmonization
IM	Intramuscular
IV	Intravenous
IDS	Investigational Drug Services
Ig	Immunoglobulin
IL	Interleukin
IND	Investigational New Drug
IRB	Institutional Review Board
ITT	Intent-To-Treat
LFT	Liver Function Tests
OSTM1	Osteopetrosis-associated Transmembrane Protein 1
PHI	Protected Health Information
PI	Principal Investigator
PP	Per Protocol
pQCT	Peripheral Quantitative Computed Tomography
RANKL	Receptor Activator of Nuclear Factor- $\kappa$ B Ligand
REPA	Report of External Professional Activities
ROM	Range of Motion
SAE	Serious Adverse Event
SDS	Standard Deviation Score
SF-36	Medical Outcomes Study Short Form-36
SST	Serum Separation Tube
SC	Subcutaneous
TBD	To Be Determined
TCIRG1	T-cell Immune Regulator 1
UMN	University of Minnesota
UPIRTSO	Unanticipated Problems Involving Risk To Subjects or Others

Interferon gamma-1b in Osteopetrosis  
USP                    United States Pharmacopeia  
vBMD                Volumetric Bone Mineral Density

## 2 Introduction / Background and Rationale

### 2.1 Description of the disease.

Osteopetrosis is a rare inherited metabolic bone disease characterized by impaired osteoclast function resulting in defective bone resorption and generalized high bone mass and mineral density (**BMD**). In patients with severe disease, this high bone mass compromises bone marrow space leading to marrow failure and frequent infections, along with hepatosplenomegaly from extramedullary hematopoiesis (1). Visual defects may result due to impingement of cranial nerves. Other sequelae include hypocalcemia and hypocalcemic seizures and “brittle bones” or osteopetrotic rickets with an increased risk of fracture (2).

Most patients with severe, autosomal recessive osteopetrosis have a defect in the osteoclast H+-ATPase proton pump; mutations affecting the production of carbonic acid and the chloride channel have been reported as well (1). The mutations result in varying degrees of osteoclast dysfunction and a wide spectrum of disease. Osteopetrosis is generally divided into three categories based on clinical aspects of disease: 1) infantile or “malignant,” inherited in an autosomal recessive fashion; 2) “intermediate,” associated with non-lethal recessive mutations, or a more severe phenotype of dominant disease; this is the patient population that will be included in this study; and 3) adult (“benign”) autosomal dominant osteopetrosis with generally milder clinical course (1). Currently, the only treatment for individuals with severe forms of osteopetrosis is hematopoietic cell transplantation (**HCT**), however survival in patients with autosomal recessive osteopetrosis treated with HCT is only around 55% (3). Therefore, this treatment is only indicated in select individuals with life-threatening complications of their disease. Clearly, additional treatments for osteopetrosis are needed both for individuals who are not candidates for HCT and to prolong the time until HCT is needed.

### 2.2 Interferon gamma-1b in osteopetrosis.

Interferon gamma is a naturally occurring cytokine that has been shown to have anti-microbial and anti-viral immunomodulatory effects (4), and is a potent stimulator of superoxide anion production which in turn promotes the formation and activation of osteoclasts (5). Interferon gamma-1b (**IFN- $\gamma$ 1b**) has been shown to increase osteoclast size, tartrate acid phosphatase staining, and superoxide anion production in cell culture from patients with osteopetrosis (6). In addition, osteopetrotic mice had increased marrow space following treatment with IFN- $\gamma$ 1b (7). Two previous studies of IFN- $\gamma$ 1b in a small group of individuals with osteopetrosis found a decrease in trabecular bone area, an increase in marrow space, a decrease in the number of severe infections requiring antibiotic therapy, and an increase in superoxide generation by granulocyte-macrophage colonies (8,9).

Despite these encouraging findings and FDA approval of interferon gamma-1b for the treatment of severe, infantile “malignant” osteopetrosis, IFN- $\gamma$ 1b is not routinely prescribed for the treatment of intermediate osteopetrosis because the FDA approval does not include this more milder form of the disease; however, many of these patients have disease progression requiring HCT just at a later age than that for the severe infantile form. Due to these issues, and the small number of patients previously treated (8,9) there is a need to further delineate who will benefit from treatment, as some osteoclast defects may be more responsive than others.

## 2.3 Significance of research

At the conclusion of this study, we will have obtained data on the tolerability and efficacy of IFN- $\gamma$ 1b that, if encouraging, will be used to increase awareness about this treatment option among clinicians taking care of patients with intermediate osteopetrosis. We expect a decrease in disease burden, and improvement in health and quality-of-life for participants in our study. Finally, the proposed project should provide further insight into possible variability in response to treatment based on genetic abnormality. These contributions are significant because there is currently no effective treatment for osteopetrosis except HCT, which carries a high mortality rate (3,10).

## 3 Interferon gamma-1b (ACTIMMUNE) Description/Indications

ACTIMMUNE® (IFN- $\gamma$ 1b), a biologic response modifier, is a single-chain polypeptide containing 140 amino acids. ACTIMMUNE is a synthetic version of IFN- $\gamma$ 1b, a naturally occurring biologic response modifier.

ACTIMMUNE is a sterile, clear, colorless solution filled in a single-use vial for subcutaneous injection. Each 0.5 mL of ACTIMMUNE contains: 100 mcg (2 million IU) of Interferon gamma-1b formulated in 20 mg mannitol, 0.37 mg disodium succinate hexahydrate, 0.14 mg succinic acid, 0.05 mg polysorbate 20 and Sterile Water for Injection. Note that the above activity is expressed in International Units (1 million IU/50 mcg). This is equivalent to what was previously expressed as units (1.5 million U/50 mcg).

ACTIMMUNE was first approved by the FDA in 1999 (Biologics License Application # 103836) and is currently FDA approved for the treatment of chronic granulomatous disease and severe malignant osteopetrosis. FDA has approved ACTIMMUNE to decrease the number and severity of infections in patients with chronic granulomatous disease and to delay the progression of severe, malignant osteopetrosis.

The original Phase 1 clinical development of ACTIMMUNE was conducted in oncology/AIDS patients and maximum tolerated doses based on intramuscular (IM) or intravenous (IV) administration were established for doses ranging from 10-1000 mcg/m^2/day. Subsequently, daily doses of 100 mcg/m^2 ACTIMMUNE by the subcutaneous (SC) route of administration was chosen based on an NCI study comparing immunological activity (including enhanced superoxide/hydrogen peroxide production) of different doses and routes of administration in melanoma patients (11). SC

administration was compared with IM administration using the 100 mcg/m^2 dose. SC administration resulted in enhanced hydrogen peroxide production and Fc receptor expression by monocytes. A comparison of two schedules, daily and three times weekly, suggested that monocyte activation may persist for up to 72 hours after ACTIMMUNE administration. Of the doses tested, 100 mcg/m^2 administered daily or three times weekly appeared to be the most effective biological response modifier regimen, and due to ease of administration, the SC route was preferred. Since then, many studies have found similar tolerability and toxicity for 100 mcg/day and 200 mcg/day (12–17). Thus, based on these previous studies of dosing safety and efficacy, we chose a maximum dose of 100 mcg/m^2 SC three times weekly for this Phase 1/2 trial.

This is an investigator-initiated, investigator-held IND, multi-institutional research study. ACTIMMUNE is FDA-approved are described above, but not for the treatment of intermediate osteopetrosis.

## 4 Study Objectives / Hypotheses

### 4.1 Primary Hypothesis

The primary hypothesis to be tested is:

That treatment with IFN- $\gamma$ 1b will be feasible and tolerable to patients with intermediate osteopetrosis.

### 4.2 Secondary Hypotheses

The secondary hypotheses are:

1. Compared to baseline, treatment with IFN- $\gamma$ 1b will result in:
  - a. Decreased tibial volumetric bone mineral density (**vBMD**) and estimated bone strength measured by peripheral quantitative computed tomography (**pQCT**);
  - b. Decreased total body and lumbar spine areal BMD (**aBMD**) by dual-energy x-ray absorptiometry (**DXA**);
  - c. Increased levels of markers of bone remodeling (see Table 1);
  - d. Increased osteoclast activity by *in vitro* testing;
  - e. Increased white blood cell (**WBC**) and platelet counts in patients that have lower than expected blood counts at baseline.
  - f. Increased height standard deviation score (**SDS**) for participants <18 years with open growth plates;
  - g. Decreased inflammation measured by erythrocyte sedimentation rate (**ESR**);

[figure not shown]
- h. Decreased pain score (based on prior 4 weeks);
  - i. Increased physical function score (based on prior 4 weeks); and
2. Compared to the 12 months prior to study entry (based on medical record review or subject recollection), treatment with IFN- $\gamma$ 1b over 12 months will result in:
  - a. Decreased number of hospitalizations for infection;
  - b. Decreased number of days treated with antibiotics;
  - c. Beneficial change in WBC and platelet counts in patients who have lower than expected blood counts at baseline;
  - d. Beneficial change in ESR;
  - e. Increased height SDS for participants  $<18$  years with open growth plates; and
3. Patients will not develop neutralizing antibodies.

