## 5.3 Evaluations and study timeline

Table 1. Evaluations and study timeline

	Screening a	Baseline	# of months from 1 st IFN- $\gamma$ 1b treatment ( $\pm$ 1 week)		
			3	6	12
General					
• Medical history	X	X	X	X	X
• Physical exam		X	X	X	X
• Genotype b		X			
• Anthropometric measurements	X	X f	X	X	X
• RNA and DNA assays		X	X	X	X
Safety Measuresc					
• Basic metabolic panel (BMP)	X	X	X	X	X
• Liver function tests (LFT)	X	X	X	X	X
• Urine pregnancy test (UPT) e	X	X	X	X	X
• Urinalysis (UA)	X	X	X	X	X
• ECHO with interpretation	X				
• EKG with interpretation	X				

• Anti-drug antibodies (ADA) g		X	X	X	X
Bone Biomarker Testingd					
• Formation Testing (bone specific alkaline phosphatase [BAP], type 1 procollagen [P1NP])	-	X	X	X	X
• Resorption testing (C-telopeptide [CTX], Tartrate resistant acid phosphatase type5b [TRAP5b])	-	X	X	X	X
• RANKL, OPG, CK-BB	-	X	X	X	X
Endocrine Assessment					
• Total 25-OH Vitamin D (25OHD) h	-	X	X	X	X
• Serum ionized calcium	-	X	X	X	X
• Urine calcium: creatinine	-	X	X	X	X
• Intact parathyroid hormone (iPTH)	-	X	X	X	X
Inflammatory/Immunology					
• CBC with differential and platelets	-	X f	X	X	X
• Erythrocyte sedimentation rate (ESR)	-	X f	X	X	X
• Immunologic phenotyping (CD3, 4, 8, 14, 15, 16, 19, 34, 56)	-	X	X	X	X
Neuropsychological testing					
• Pain assessment	-	X	X	X	X
• Quality of life survey	-	X	X	X	X
Orthopedic assessment					
• Dual energy X-ray absorptiometry (DXA) lumbar spine, total body, total hip and femoral neck (adults $\geq 18$ yrs only)	-	X	-	-	X
• Peripheral Quantitative CT (pQCT) left tibia	-	X	-	X	X
In vitro osteoclast function assays – [name] Lab					
• Gene expression – osteoclast marker genes	-	X	X	X	X
• Osteoclast activity – ability to release calcium phos from coated plate	-	X	X	X	X
Infectious outcomes					
• Number of hospitalizations in prior 3 months	-	X f	X	X	X
• Number of days treated with antibiotics in last 3 months	-	X f	X	X	X
• Type of infectious organism	-	X f	X	X	X
RANKL=Receptor activator of nuclear factor kappa-B ligand; OPG=osteoprotegerin; CK-BB=creatinine kinase isoenzyme BB.					
a Screening visit evaluations will count for baseline evaluations where applicable. Screening visit will be within 3 months of baseline visit					

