## 7.2 Statistical Methods

### 7.2.1 Sample size Determination

This is a pilot study to obtain data for a larger, definitive clinical trial. The sample size of 10 was determined based on feasibility estimates including potential screening failures

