### 7.2.2 Statistical Analysis

Descriptive analyses of baseline characteristics and outcomes will include means and standard deviations for continuous variables and frequencies for categorical variables. Confidence intervals and P-values will be based on a t-distribution. Statistical significance will be considered as  $p < 0.05$ . The primary endpoint and safety analyses will be primarily descriptive reporting the number and percentage of compliance and AEs. The secondary endpoints for hematologic function, immune function, and bone mineral density will be evaluated by paired t-tests or chi-squared to evaluate change from baseline to 12 months. Secondary endpoints related to in vitro osteoclast assays will be descriptive.

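### Hypothesis 1e selects subjects for a low baseline WBC or platelet count and tests the change from that same baseline in a single arm, so regression to the mean alone can give a significant rise

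*Combined protocol and SAP*

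**What the plan says.** Section 4.2 has two hypotheses on blood counts. Hypothesis 1e compares with baseline and is limited to "patients that have lower than expected blood counts at baseline". Hypothesis 2c reads "Beneficial change in WBC and platelet counts in patients who have lower than expected blood counts at baseline", but its comparator is different: "Compared to the 12 months prior to study entry (based on medical record review or subject recollection"). Neither gives a cut-off for a low count.

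Section 7.2.2 says that the secondary endpoints for hematologic function, among others, "will be evaluated by paired t-tests or chi-squared to evaluate change from baseline to 12 months". It adds "Confidence intervals and P-values will be based on a t-distribution" and sets the threshold: "Statistical significance will be considered as" p<0.05. It does not repeat the restriction to low-count subjects, and it describes no separate test against the prior 12 months.

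The trial has one arm (Study Summary) and 10 subjects. In Table 1 (Section 5.3) the CBC row has a dash at Screening, then entries at Baseline and months 3, 6 and 12. Footnote f, attached to the Baseline entry, says that the CBC comes from the medical record when available. Section 6.3.2 has the CBC run in real time at baseline, 3, 6 and 12 months. Neutropenia and thrombocytopenia are two of the five alternative qualifying criteria in Section 5.4.5.

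**The concern.** A measured count is the subject's usual level plus day-to-day variation and assay error. Subjects picked because one reading is low tend to have been picked partly for a downward chance deviation. That deviation is not expected to recur at month 12, so the mean change is positive even if the drug does nothing. A concurrent control arm would show the same drift and allow it to be subtracted, but this trial has none. The plan also names no baseline-adjusted analysis, no averaged baseline, and no WBC or platelet hypothesis covering all subjects.

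The bias runs towards the hoped-for result. Section 2.3 intends encouraging efficacy data to raise clinicians' awareness of the treatment, and Section 7.2.1 intends the pilot to supply data for a definitive trial. An inflated count response would feed both.

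**Working it through.** **The plan's own figures.** There is no power calculation to reproduce: "The sample size of 10 was determined based on feasibility estimates including potential screening failures". The stated threshold is 0.05. Sidedness is not stated. Taking it as two-sided, the nominal chance of a false significant rise is 0.05/2 = 2.5%.

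**Assumptions, none of them in the documents.** Counts are on a standardised normal scale. There is no drug effect. The correlation between baseline and month 12 is ρ = 0.5 to 0.95. Subjects enter the subgroup if baseline lies below c, with c = -0.5 or -1 SD. The subgroup size is n = 3 to 8.

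**Expected spurious rise.** With X the baseline count and Y the month-12 count, E(Y − X | X < c) = (1 − ρ) × φ(c)/Φ(c).

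- c = -0.5: φ/Φ = 0.3521/0.3085 = 1.141
- c = -1: φ/Φ = 0.2420/0.1587 = 1.525
- Example: c = -1 and ρ = 0.7 give 0.3 × 1.525 = 0.46 SD

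**Chance of a significant rise.** I simulated 200,000 trials per cell, drawing X below c, setting Y = ρX + √(1 − ρ²)·e, and applying the paired t-test with its upper tail at 2.5%.

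| c (SD) | ρ | Expected rise (SD) | n=3 | n=5 | n=8 |
|---|---|---|---|---|---|
| -0.5 | 0.95 | 0.06 | 4.0% | 5.0% | 6.6% |
| -0.5 | 0.9 | 0.11 | 4.8% | 6.7% | 9.2% |
| -0.5 | 0.7 | 0.34 | 7.3% | 12.6% | 20.8% |
| -0.5 | 0.5 | 0.57 | 9.8% | 19.2% | 33.7% |
| -1 | 0.95 | 0.08 | 4.7% | 6.3% | 8.7% |
| -1 | 0.9 | 0.15 | 5.8% | 8.8% | 13.4% |
| -1 | 0.7 | 0.46 | 9.9% | 19.2% | 33.6% |
| -1 | 0.5 | 0.76 | 14.3% | 30.9% | 54.8% |

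**How plausible the larger subgroups are.** Without enrichment, the expected number below the cut is 10 × 0.3085 = 3.1 subjects at -0.5 SD and 10 × 0.1587 = 1.6 at -1 SD. The binomial chance of 8 or more of 10 below -1 SD is about 0.00001. If the subgroup is drawn from 10 unselected subjects and tested when at least 3 qualify, the false-rise rate is 3.8% to 16.6% (lowest 20%, 50% or 80% selected; ρ from 0.5 to 0.9).

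**Hypothesis 2c.** If the comparator is a prior-year count independent of the selecting value, the rate is 2.4–2.6%, which is nominal. If the comparator averages one prior-year count with the selecting baseline value, the rate is 2.9% to 21.8% (lowest 20%, 50% or 80% selected; ρ from 0.5 to 0.95; n = 5 or 10).

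**Effect of the fix.** Selecting on one pre-treatment count and computing change from a second, with independent errors, gives a mean change of zero and a rate of about 2.5% in every setting run.

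**The case against.** Much can be said on the other side, and several stronger readings do not hold.

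- **A reader might infer that 2c has the same flaw as 1e.** As worded, 2c compares with the prior 12 months. It is biased only if the selecting baseline value is, or is part of, that comparator, or if the baseline to month-12 test is applied to it for want of any other. The documents do not say which.
- **A reader might infer that the analysis section commits to testing low-count subjects only.** It does not. The restriction stands in the hypotheses, and Section 7.2.2 is silent on which subjects are tested. Even so, 1e as written is a claim about the subgroup, and a test of 1e has to be made there.
- **A reader might cite footnote a of Table 1, "Screening visit evaluations will count for baseline evaluations where applicable", to show that the qualifying count doubles as baseline.** It does not show this, because Table 1 has no Screening CBC to carry over. Section 5.4.3 has eligibility confirmed from medical records, so the qualifying count may be separate from the Baseline draw. That does not rescue 1e, which selects on the baseline count itself.
- **The size may be modest.** If counts are very stable, if most subjects qualify, or if only 3 or 4 are analysed, the excess is small. It vanishes if the selected subjects truly lie far below the cut. All of this stands. The plan offers no evidence for any of these conditions.
- **These are secondary endpoints of a 10-subject pilot.** This also stands, and it limits the consequence. But the plan attaches a significance threshold to them.

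**Conclusion.** The point holds for hypothesis 1e. Selection and change score share one baseline value, there is no control arm, and the planned test makes no allowance for this. For 2c it holds only under the conditions given above.

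The direction of the bias is certain whenever the correlation is below 1 and the cut falls within the spread of counts. Its size cannot be fixed from the documents. Under the stated assumptions the false-rise rate is about 4–9% at correlation 0.95, 5–13% at 0.9, 7–34% at 0.7 and 10–55% at 0.5, against 2.5%. A reader might take the highest figures as typical. They are not: they need most of the 10 subjects below the cut, which requires eligibility to enrich for low counts, and only some of the qualifying criteria do that. The primary feasibility and tolerability conclusion does not depend on this.

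**What to change.** 1. Define a low WBC count and a low platelet count in advance, by age where needed.
2. Assign the low-count subgroup from a pre-study medical-record count, which footnote f already collects when available. Compute change from a separate pre-dose Baseline CBC (Section 6.3.2) that was used neither for eligibility nor for subgroup assignment.
3. Clarify footnote f so that a record value does not replace the Baseline draw.
4. For 2c, state the test, and compare with prior-12-month counts that exclude the selecting value.
5. Also report the change in all treated subjects. A reader might think this alone is enough. It reduces the bias but does not remove it, because Section 5.4.5 itself admits subjects on low counts.

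The cost is mostly wording, with one operational demand: sites must take the Baseline CBC in every subject. Subjects with no separate pre-study count drop out of the subgroup analysis, and 2c needs at least one further record count. The return to the nominal rate assumes that the two pre-treatment counts have independent errors, so a record count taken close to the Baseline draw would serve less well.
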